9.8 Notification of Post-Study Serious Adverse event

Investigators are not obligated to actively seek follow-up information for subjects with an adverse event after the conclusion of the study (i.e. >180-200 days after the FMT procedure). However, if the investigator becomes aware of an adverse event that occurs after the subject completes and the adverse event is recognized by the Investigator to be at least possibly related to study procedure, the investigator must notify the University of Texas Health Science Center IRB and FDA within 15 calendar days of making the determination about the event.

9.9 Grading Adverse Event Severity

Adverse Events are to be graded by severity by the site investigator following FDA guidelines

(<http://www.fda.gov/downloads/BiologicsBloodVaccines/GuidanceComplianceRegulatoryInformation/Guidances/Vaccines/ucm091977.pdf>). For the classification of adverse events, severity is not the same as seriousness, which is defined in section 9.6. Severity is an indication of the *intensity* or a specific event (e.g., mild, moderate or severe). Classification of an event as serious relates to an event's outcome or intervention criteria and is usually associated with events that pose a threat to a

subject's life or functioning (Severity Grading Table). An event can be severe but not serious, such as a migraine. Using the definitions in Severity Grading Table at the end of the protocol, the site investigator will categorize the severity of an adverse event on the AE reports.

9.10 Halting Criteria

Halting will take place if a serious adverse event is seen that is at least possibly related to FMT and if there is any suspected or confirmed transmission of a pathogen from the product to a study subject. The study will be halted temporarily until the DSMB makes a decision. Halting will also take place if the DSMB is concerned enough to stop the study to collect and analyze more clinical data.

If a subject develops infection after FMT caused by a bacterial pathogen (e.g. urinary tract infection, sepsis, pneumonia), any potential pathogen isolated by a laboratory (e.g. *E. coli* from urinary tract) will be obtained if at all possible and compared with the same species identified from the donor using either culture or ribotyping techniques to determine if the FMT was responsible for transmission of a bacterium from the product to a subject. A form will be given to subjects to provide to their doctors if an infection is diagnosed after FMT, requesting to work with their laboratory to send the isolate to the University of Texas School of Public Health at [name] for further study. The research program will pay for any reasonable costs for obtaining and shipping of the bacteria.

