DEFINITION OF TREATMENT FAILURE	Treatment failure is defined as the presence of diarrhea (passage of ≥ 3 watery stools per 24-hour period for two consecutive days) and C. difficile toxin A/B positive stool within 60 days of FMT treatment plus receipt of anti- C. difficile antibiotics.
STUDY AGENT, DOSE OF ADMINISTRATION	
Processed intestinal bacteria from a screened healthy donor will be administered lyophilized FMT to be given by the oral route. FMT will be given as follows:
 
 1. Group 1: With bowel prep and Imodium 1st treatment day, lyophilized product generated from 50g of stool 2nd treatment day, lyophilized product generated from 50g of stool 2. Group 2: With bowel prep and Imodium 1st treatment day, lyophilized product generated from 100g of stool 2nd treatment day, lyophilized product generated from 50g of stool 3. Group 3: With bowel prep and Imodium 1st treatment day, lyophilized product generated from 100g of stool 2nd treatment day, lyophilized product generated from 100g of stool 4. Unblinded Group 4: (Without bowel prep and Imodium) 1st treatment day, lyophilized product generated from 100g of stool 2nd treatment day, lyophilized product generated from 100g of stool
EFFICACY EVALUATION	
Primary Endpoint:
 
 • Safety of FMT (lyophilized capsules with various doses) • Prevention of subsequent bouts of CDI in 60 days post FMT. • Safety of FMT (lyophilized capsules with same doses) without using pre-FMT bowel preparation and Imodium • Prevention of subsequent bouts of CDI in 60 days post FMT without using pre-FMT bowel preparation and Imodium. 
Secondary Endpoint:
 
 • To characterize improvement in microbiota diversity from baseline in subjects treated with various doses of lyophilized capsules.

SAFETY EVALUATION	To ensure safe study conduct during the study, an independent, non-blinded, external Data and Safety Monitoring Board (DSMB) will be established to perform safety evaluations on an ongoing basis. A DSMB charter will be developed and will detail the review of the safety data. The DSMB will have the power to stop the trial.
STUDY STOPPING RULES	Study may be halted or discontinued if the DSMB identifies a trend of more illnesses or side effects in one or more of the treatment groups.

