3.4 Data Safety and Monitoring Board

A committee of 3 faculty level people will serve as the DSMB reviewing primary and

secondary parameters and data from the study. Safety will be the greatest concern. The DSMB has the capacity to stop the study. The Board will meet at least three times during the study: At the study beginning; after 8-10 patients in each group have been studied and at the completion of the study (all subjects reached 180-200 days follow-up after FMT).

Professional	Name
Pharmacist	[name]
Epidemiologist	[name]
Clinical Infectious Diseases Specialist	[name]

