4.9 Termination of Study

Although the Principal Investigator has every intention of completing the study, he may terminate the study at any time for clinical, safety or administrative reasons.

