9. ASSESSMENT OF SAFETY AND EFFICACY

9.1 Assessment of Safety (Definition)

9.1.1 Adverse event:

Any untoward medical occurrence associated with the use of PRIM-DJ2727 whether or not considered drug related, and can therefore be

- Any symptom not previously reported by the subjects (medical history/pre-treatment diary). Wherever possible, a specific disease rather than individual associated signs and symptoms should be identified by the investigator. However, if an observed or reported sign or symptom is not considered a component of a specific disease by the investigator, it should be recorded as a separate adverse event.
- Clinical worsening of baseline parameters according to subject.
- A condition felt to be possibly related to treatment first detected or diagnosed after study drug administration

All adverse events (AEs) that occur within 180-200 days after treatment will be recorded as indicated above. Recurrence of CDI is not to be recorded as an adverse event unless hospitalization ≥ 24 hours is required for management, then recorded as serious adverse event.

9.1.2 Suspected adverse reaction:

Any adverse event for which there is a reasonable possibility that the study drug caused the adverse event. For the purposes of IND safety reporting, "reasonable possibility" means

there is evidence to suggest a causal relationship between the drug and the adverse event.

9.1.3 **Serious adverse event:**

Any adverse event or suspected adverse reaction is considered serious if in the view of the investigators it results in any of the following outcomes:

- Death
- Life-threatening adverse event
- Hospitalization \geq 24 hours
- Prolongation of existing hospitalization
- Substantial disruption of the ability to conduct normal life functions
- Congenital abnormally/birth defect
- Important medical events that jeopardize the patient, such as allergic bronchospasm requiring intensive treatment
- Persistent or significant incapacity or substantial disruption of the ability to conduct normal life functions

An emergency room visit without hospital admission will not be recorded as a serious adverse event (SAE) under this criterion, nor will hospitalization for a procedure scheduled or planned before signing of informed consent.

Death and life-threatening AEs possibly related to the study are reported by study coordinator or investigator within 24 hours to the IRB. Other SAEs potentially related to the study will be reported to the IRB within 7 days.

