9.7 Investigator Reporting of Suspected Unexpected Serious Adverse event (SUSAR)

Adverse events that meet all three definitions described above of a Suspected (related or possibly related to study drug or participation in the research), Unexpected and Serious Adverse Reaction (SUSAR) must be reported to the University of Texas Health Science IRB and FDA expeditiously. The investigator must report an adverse event as a suspected adverse reaction only if there is evidence to suggest a causal relationship between the drug and the adverse event.

The investigator must report all suspected unexpected serious adverse reaction events to the University of Texas Health Science IRB/CPHS via iRIS within 7 calendar days after investigator recognizes or classifies the event as SUSAR unless the report involves the death of a participant, in which case the event needs to be reported to IRB within 24 hours after first knowledge by the investigator via facsimile or email or by telephone.

The investigator must also report all suspected unexpected serious adverse reactions to the FDA as soon as possible but within a maximum of 15 calendar days of first knowledge by the investigator, unless the event is *unexpected fatal or life-threatening suspected adverse reaction*, in which case the event needs to be reported to the FDA as soon as possible but in no case later than 7 calendar days after the investigator's initial receipt of the information.

The reports should identify the subject by their unique subject number instead of names. The completed serious adverse event report forms will be used by the investigators in regulatory filings. The investigator is responsible for continuing to report to the University of Texas Health Science IRB and FDA within 15 calendar days of any new or relevant follow-up information obtained concerning the SUSAR event. The results of any additional assessments conducted must also be reported to the University of Texas Health Science IRB and FDA.

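### Section 9.10 joins its two automatic halting triggers with 'and if', so read literally neither a possibly related SAE nor pathogen transmission pauses the trial on its own

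*Combined protocol and SAP*

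**What the plan says.** Section 9.10 (Halting Criteria) calls for a halt on an SAE which "is at least possibly related to FMT and if there is any suspected or confirmed transmission of a pathogen from the product", meaning transmission to a recipient. The consequence follows: "The study will be halted temporarily until the DSMB makes a decision". A third route is a matter of judgement: "Halting will also take place if the DSMB is concerned enough to stop the study" in order to gather and analyse more data. The second paragraph of 9.10 describes how bacterial infections after FMT, with urinary tract infection among the examples, are to be compared with donor isolates.

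Elsewhere:

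- **Synopsis, Safety Evaluation and Study Stopping Rules.** An external, non-blinded DSMB "will be established to perform safety evaluations on an ongoing basis" and can stop the trial. The stopping rule is permissive and rests on a trend in illnesses or side effects. It names neither 9.10 trigger.
- **Section 3.4.** The DSMB meets at least three times: at the start, then "after 8-10 patients in each group have been studied and at the completion of the study".
- **Section 4.9.** The Principal Investigator keeps the option to end the study: "he may terminate the study at any time for clinical, safety or administrative reasons".
- **Section 9.1.3.** Possibly related deaths and life-threatening events go to the IRB within 24 hours. For the rest, "Other SAEs potentially related to the study will be reported to the IRB within 7 days".
- **Section 9.7.** SUSARs "must be reported to the University of Texas Health Science IRB and FDA expeditiously". The DSMB is not named as a recipient.

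**The concern.** A rule of the form 'halt if A and if B' is met only when A and B both hold. Here A is an SAE at least possibly related to FMT and B is suspected or confirmed transmission of a pathogen from the product. Read that way, a death judged possibly related to the capsules, with no suspicion of transmission, does not trigger the pause. Nor does confirmed transmission that causes only a non-serious infection. Staff who carried on dosing in either case would be following the text.

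What is at stake is patient safety between DSMB meetings. Section 9.10 is the only provision in these documents that makes a pause mandatory when a particular event occurs and sends the question to the DSMB. The other routes depend on the event reaching the DSMB or on one person's judgement, and the SAE and SUSAR reporting sections name only the IRB and FDA.

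**Working it through.** The plan states no figure to reproduce. The point turns on wording, so the first two steps are logical. The third only illustrates scale.

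**1. When the readings differ**

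| Events so far | Pause under 'and' | Pause under 'or' |
|---|---|---|
| Neither A nor B | No | No |
| A only (possibly related SAE) | No | Yes |
| B only (transmission) | No | Yes |
| Both A and B | Yes | Yes |

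They differ only when exactly one trigger has occurred.

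**2. Does another section settle the reading?**

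- Synopsis stopping rule: permissive, based on a trend, names neither trigger.
- Section 3.4: sets a minimum number of meetings and says nothing about single events.
- Section 4.9: an option for the Principal Investigator, not a rule.
- Sections 9.1.3, 9.6 and 9.7: recording and reporting duties only. Section 9.6 gives the DSMB a final report on related events but no notice of each one.
- Section 9.10, third sentence: a halt at the DSMB's discretion.

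None says that A alone or B alone pauses the study.

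**3. Illustrative size**

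Inputs from the documents: 360 subjects in four groups (section 3); an interim DSMB meeting after 8-10 per group (section 3.4).

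- Studied by that meeting: 4 × 8 = 32 to 4 × 10 = 40.
- Still to come: 360 − 40 = 320 (88.9%) to 360 − 32 = 328 (91.1%).

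Assumed, because the documents give no rates: *p*, the chance that a subject has a possibly related SAE (0.2%, 0.5%, 1%); and *q*, the share of those SAEs that also involve suspected transmission (10% to 30%).

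For *n* = 320 and independent subjects, the chance of at least one SAE-triggered automatic pause is 1 − (1 − *p*)^320 under 'or', and 1 − (1 − *pq*)^320 under 'and'.

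| *p* | 'Or' | 'And', *q* = 10% | 'And', *q* = 30% |
|---|---|---|---|
| 0.2% | 1 − 0.998^320 = 0.473 | 1 − 0.9998^320 = 0.062 | 1 − 0.9994^320 = 0.175 |
| 0.5% | 1 − 0.995^320 = 0.799 | 1 − 0.9995^320 = 0.148 | 1 − 0.9985^320 = 0.381 |
| 1% | 1 − 0.99^320 = 0.960 | 1 − 0.999^320 = 0.274 | 1 − 0.997^320 = 0.618 |

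With *n* = 328 the 'or' column becomes 0.481, 0.807 and 0.963. The 'and' columns count an SAE and suspected transmission in the same event. Transmission without an SAE is left out; under 'or' it would be a further trigger and widen the gap.

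**The case against.** The best reply is that 'and if' is ordinary English for listing two separate conditions. Each has its own 'if', and the paragraph goes on to list a third. The conjunctive reading also fits the section poorly. Transmission is qualified by 'any'. An SAE that arose from suspected transmission would already be possibly related, so that qualifier would add little. And the second paragraph investigates infections with no seriousness threshold. On this view the defect is editorial. The DSMB and the Principal Investigator can still stop the study, and the DSMB charter, which is not available here, may set out how events reach the board. The probabilities rest on assumed rates and make no allowance for how unlikely staff are to apply the literal reading.

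Much of this stands. Either/or is the more likely intent, the discretionary routes remain, and the figures are no evidence that the trial would run under 'and'. Section 3.4 sets only a minimum number of meetings, so the interim meeting is not a firm boundary. But none of this makes the sentence say 'or', and no other section supplies the missing rule. A mandatory safety rule should not depend on staff inferring a different connective from the one printed.

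**Conclusion.** The concern holds. Followed as written, the automatic pause in section 9.10 needs both a possibly related SAE and pathogen transmission, and nothing else in the documents makes either one sufficient. The loss is confined to the automatic pause for single-trigger events; discretionary halts survive under either reading.

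The conclusion rests on the wording alone and needs no assumed rate. On the ranges assumed above, the chance of an SAE-triggered pause among 320 later subjects is 47%-96% under 'or', against 6%-62% under 'and'. Those figures show how far the readings could diverge and do not predict what would happen. The sponsor should correct the rule. Confidence is medium, because either/or was probably intended and the charter may already cover notification.

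**What to change.** Replace 'and if' with 'or if' in section 9.10 or, better, number the triggers:

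1. any SAE at least possibly related to FMT;
2. any suspected or confirmed transmission of a pathogen from the product to a subject.

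Then state that either one alone temporarily halts enrollment and dosing until the DSMB decides, and that the investigator notifies the DSMB when a trigger occurs. A cross-reference to 9.10 from the synopsis stopping rule would help but is optional.

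The cost is one word, or a short list and a sentence on notification. The downside is possibly more temporary pauses, which were already part of the plan if either/or was the intent. Sample size and analysis are unaffected.

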9.11 Efficacy Endpoint

The primary endpoints of the study are to evaluate the safety of lyophilized product by capsules with various doses and the prevention of subsequent bouts of CDI in 60 days post FMT; and to evaluate the safety of lyophilized product by capsules with same doses without bowel preparation and Imodium, and the prevention of subsequent bouts of CDI in 60 days post FMT without bowel preparation and Imodium. The secondary endpoint is to characterize improvement in microbiota diversity from baseline in subjects treated with various doses of lyophilized capsules.

9.12 Stool Analysis

Stool samples for future metagenomics/microbiome analysis will be collected before FMT and at follow up days 1, 7, 14, 30, 60 and 90 and unscheduled visit (if any up to 60 days) after FMT treatment. Stool samples collected up to 60 days after FMT treatment including unscheduled specimen (if any) will be tested for *C. difficile* toxins A/B at EPDL in weekly batches. All collected stool samples will be stored at -80°C. Procedures for

stool sample collection and handling storage will be recorded.

10. DATA COLLECTION AND ANALYSIS

10.1 Recording of Data

The Investigator and/or designee must maintain adequate and accurate study related documents including source documents and regulatory documents. The study documents will be reviewed and signed by the investigators periodically. Study records will remain on file for a minimum of two years after the completion/termination of this study.

10.2 Statistical Methods

10.2.1 General Considerations

All analyses will be performed, and all tables, figures, and data listings will be prepared using SAS (Cary, NC). Summary statistics for continuous variables will include the mean, standard deviation, median, minimum, and maximum value; categorical variables will be presented as counts and percentages. For all analyses, baseline is defined as the date of fecal transplantation.

10.2.2 Power Calculations

Assuming recipients receiving 100g for both treatment days, 100g on the first treatment day and 50g on the second treatment, or 50g for both treatment days, or 100g for both treatment days without bowel prep and Imodium has 88%, 80%, 70% and 80% efficacy in preventing post RCDI respectively, it is determined that 348 recipients (1:1:1:1 ratio) would provide 85% power to detect a statistically significant difference in the distributions of efficacy between the 4 treatment groups at the two-sided $\alpha = 0.05$ level of significance. Assuming 10% of patients would be lost to follow-up, 360 (90 in each group) recipients are planned.

10.2.3 Analysis Populations

Two primary analyses will be performed:

- 1) Analysis for safety and efficacy between three groups (1-3) receiving varied doses of lyophilized product generated from stool (50g for both treatment days; 100g on the first treatment day and 50g on the second treatment; 100g for both treatment days)
- 2) Analysis for safety and efficacy between two groups (3 and 4) with and without bowel preparation and Imodium receiving same high doses of lyophilized product (100g for both treatment days).

- All analyses will be conducted using the intent-to-treat population. Intent-to-treat is defined as all subjects who have started the procedure.
- Listings and summary tables with descriptive statistics will be prepared for demographic data (gender, date of birth, race/ethnicity), and medical history data.

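### The stated 85% power belongs to a 4-group comparison that is not a listed primary analysis and does not reproduce; the primary group 3 versus 4 comparison has about 28-31% power for the 8-point loss that the plan assumes

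*Combined protocol and SAP*

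**What the plan says.** Section 10.2.2 (Power Calculations) assumes that the regimens, in the order 100g/100g, 100g/50g, 50g/50g and 100g/100g without preparation (groups 3, 2, 1 and 4), "has 88%, 80%, 70% and 80% efficacy in preventing post RCDI respectively". It concludes that 348 recipients "would provide 85% power to detect a statistically significant difference in the distributions of efficacy between the 4 treatment groups", at two-sided 0.05. It then adds: "Assuming 10% of patients would be lost to follow-up, 360 (90 in each group) recipients are planned".

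Section 10.2.3 (Analysis Populations) states "Two primary analyses will be performed". The first compares safety and efficacy across the three dose groups 1 to 3. The second is "Analysis for safety and efficacy between two groups (3 and 4) with and without bowel preparation and Imodium", both at the higher dose. The Synopsis and sections 2 and 9.11 also place the comparison without preparation among the primary endpoints.

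Section 10.2.6 (Efficacy Analyses) names no specific test. It refers back to standard analyses and says that the investigators expect trends and not statistical significance. The plan states no multiplicity rule, and no equivalence or non-inferiority margin.

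**The concern.** A reader of section 10.2.2 would take 85% as the trial's power for its primary efficacy questions. It attaches to neither of them. The 4-group comparison is driven mostly by the gap between 70% and 88% (group 1 versus group 3), and it does not isolate the effect of preparation and Imodium.

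Group 3 versus 4 is where this matters most. The plan itself assumes that efficacy is 8 points lower without preparation. If that is true and the analysis usually returns a non-significant result, the result is open to being read as no difference. Nothing in the plan says how a null result on this comparison is to be interpreted, and the only power figure on the page suggests that the trial could have found a difference.

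**Working it through.** **Inputs.** Rates of 88%, 80%, 70% and 80%, two-sided 0.05, and 348 recipients (87 per group) all come from section 10.2.2. The planned number is 90 per group. If the plan's 10% loss occurs, 360 × 0.9 = 324 remain, or 81 per group. Because no test or multiplicity rule is given, I assume Pearson chi-square tests at an unadjusted two-sided 0.05.

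**Step 1: the plan's own figure (4 groups, 3 df).** The noncentrality is λ = n × Σ(p − p̄)² / [p̄(1 − p̄)].
- p̄ = (0.88 + 0.80 + 0.70 + 0.80)/4 = 0.795
- Σ(p − p̄)² = 0.007225 + 0.000025 + 0.009025 + 0.000025 = 0.0163
- λ/n = 0.0163/(0.795 × 0.205) = 0.1000

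At 87 per group λ = 8.70 and power is 69.5% (simulation 69.8%; likelihood-ratio version 69.9%; arcsine version 70.5%). The stated 85% is not reproduced. It would need about 123 per group, 492 in all.

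Values near 85% arise only from other calculations: a trend test over groups 1 to 3 (83.9% at 87 per group, 85.1% at 90), group 1 versus group 3 (83.6% and 84.9%), or three groups of 116 (86.9%). The documents do not show which, if any, was used.

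**Step 2: primary analysis 1 (groups 1 to 3, 2 df).**
- p̄ = 2.38/3 = 0.7933
- Σ(p − p̄)² = 0.01627
- λ/n = 0.01627/(0.7933 × 0.2067) = 0.0992

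**Step 3: primary analysis 2 (group 3 versus 4, 88% versus 80%).** Power = Φ{[0.08√n − 1.96√(2 × 0.84 × 0.16)] / √(0.88 × 0.12 + 0.80 × 0.20)}. At n = 90 this is Φ[(0.759 − 1.016)/0.515] = Φ(−0.499) = 30.9%.

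| Comparison | 81 per group | 87 per group | 90 per group |
|---|---|---|---|
| 4 groups | 66.0% | 69.5% | 71.1% |
| Groups 1 to 3 | 72.0% | 75.2% | 76.7% |
| Group 3 versus 4 | 28.3% | 30.0% | 30.9% |

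Exact enumeration for group 3 versus 4 at 87 to 90 per group gives 29.6-30.7% (chi-square) and 23.6-24.6% (Fisher). Splitting alpha to 0.025 gives 19.6% (81 per group) to 21.7% (90). Reaching 80% power would need 329 per group.

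**Step 4: how far the low power extends.** Power for group 3 versus 4 from 88%, at 81 to 90 per group:

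| True loss | Power |
|---|---|
| 8 points | 28-31% |
| 10 points | 39-43% |
| 12 points | 51-55% |
| 15 points | 68-72% |
| 18 points | 81-85% |

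**Step 5: precision of group 3 versus 4 (95% half-width).**
- Observed 88% versus 80%: 1.96√[(0.1056 + 0.16)/n] = 10.6 points at 90 per group, 11.2 at 81.
- Zero observed difference at a common 88%: 1.96√(0.2112/n) = 9.5 and 10.0 points.
- Zero observed difference at a common 84%: 1.96√(0.2688/n) = 10.7 and 11.3 points.

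At these rates a zero observed difference leaves an 8-point loss inside the interval. That would change only at clearly higher common rates: at 92% and 90 per group the half-width is 1.96√(0.1472/90) = 7.9 points.

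**The case against.** The strongest reply is that this is a Phase II study whose Synopsis calls efficacy preliminary, and that section 10.2.6 already disclaims statistical significance. That is fair as context and softens any charge of concealment. It does not resolve the problem. The disclaimer conflicts with a claim of 85% power, and it does not say how a non-significant group 3 versus 4 result is to be read.

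Four stronger readings are tempting, and the documents do not support them.
- A reader might infer that any real loss without preparation would usually be missed. Step 4 shows otherwise: power passes 50% between 10 and 12 points and exceeds 80% at 18.
- A reader might apply the half-width of 10.6 points to a zero observed difference and say that a 10-point loss could never be excluded. That width belongs to unequal rates. At a common 88% with 90 per group the half-width is 9.5 points, which does exclude 10.
- A reader might say that the 4-group test is never run. Section 10.2.6 points back to analyses outlined above it, which could include that test. The text supports only that section 10.2.3 does not list it as primary.
- A reader might infer that the sponsor plans to claim equivalence. No such claim or margin appears. The risk lies in how a null result may be read.

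Safety is also a primary aim of the group 3 versus 4 comparison, and this point does not bear on it.

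**Conclusion.** The point holds for efficacy. The only power figure is for a comparison that is not a listed primary analysis, and it is about 15 percentage points too high for that comparison (about 70% at 87 per group, 71% at 90, 66% at 81). The two declared primary analyses have about 72-77% power (groups 1 to 3) and about 28-31% (group 3 versus 4).

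An 8-point loss in group 4, which is the plan's own assumption, would be non-significant about 7 times in 10. This should not be extended to losses well above 11 points. A null group 3 versus 4 result, at common rates of 84% to 88%, would not exclude that 8-point loss.

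These figures rest on the plan's assumed rates, chi-square tests, 81 to 90 analysed per group, and no multiplicity adjustment. A Fisher test or an alpha split would lower the group 3 versus 4 figure further.

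**What to change.** No extra subjects are needed.

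**Section 10.2.2.** Replace the 85% with the power or precision of each primary analysis: groups 1 to 3, about 72-77%; group 3 versus 4, about 28-31%, with a 95% half-width of about 11 points at the assumed rates. If the 4-group figure is kept, restate it as about 70%. If the 85% came from a different test, name that test and make it part of the planned analysis.

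**Section 10.2.6.**
- Reconcile the expectation of trends only with the power statement.
- Name the efficacy tests.
- Report the group 3 versus 4 risk difference with its 95% confidence interval as an estimate.
- State that a non-significant result will not be read as evidence that efficacy is unchanged without preparation and Imodium.

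If the sponsor wants to conclude that efficacy is no worse, that needs a justified margin and its own sample size. This is a separate choice for the sponsor.

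**Cost.** Two paragraphs of protocol wording, best settled before outcome data are seen. The downside is that the stated power becomes less favourable.
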